10.3.2. Definition of SAE

| |
|---|
| An SAE is an AE that: |
| 1. Results in death |
| 2. Is life-threatening 
• The term life-threatening in the definition of serious refers to an event in which the participant was at risk of death at the time of the event. It does not refer to an event, which hypothetically might have caused death, if it were more severe. |
| 3. Requires inpatient hospitalization or prolongation of existing hospitalization 
• In general, hospitalization signifies that the participant has been admitted (usually involving at least an overnight stay) at the hospital or emergency ward for observation and/or treatment that would not have been appropriate in the physician's office or outpatient setting. Complications that occur during hospitalization are AEs. If a complication prolongs hospitalization or fulfills any other serious criteria, the event is serious. When in doubt as to whether hospitalization occurred or was necessary, the AE should be considered serious.• Hospitalization for elective treatment of a pre-existing condition that did not worsen from baseline is not considered an AE. |
| 4. Results in persistent or significant disability/incapacity 
• The term "disability" means a substantial disruption of a person's ability to conduct normal life functions.• This definition is not intended to include experiences of relatively minor medical significance, such as uncomplicated headache, nausea, vomiting, diarrhea, influenza, and accidental trauma (eg, sprained ankle), that may interfere with or prevent everyday life functions but do not constitute a substantial disruption. |
| 5. Is a congenital anomaly/birth defect |
| 6. Other situations 
• Medical or scientific judgment should be exercised by the Investigator in deciding whether SAE reporting is appropriate in other situations, such as significant medical events that may jeopardize the participant or may require medical or surgical intervention to prevent one of the other outcomes listed in the above definition. These events should usually be considered serious.• Examples of such events include invasive or malignant cancers, intensive treatment for allergic bronchospasm, blood dyscrasias, convulsions, or development of drug dependency or drug abuse. |

10.3.3. Recording and Follow-up of AE or SAE

AE and SAE Recording

- When an AE/SAE occurs, it is the responsibility of the Investigator to review all documentation (eg, hospital progress notes, laboratory reports, and diagnostics reports) related to the event.
- The Investigator will then record all relevant AE/SAE information using the AE/SAE Form and the AE section of the eCRF.
- It is **not** acceptable for the Investigator to send photocopies of the participant's medical records to EQRx International, Inc. and Parexel Pharmacovigilance Group in lieu of completion of the SAE Form.
- There may be instances when copies of medical records for certain cases are requested by both EQRx International, Inc. and Parexel Pharmacovigilance Group. In this case, all participant identifiers, with the exception of the participant number, will be blinded on the copies of the medical records before submission to EQRx International, Inc. and Parexel Pharmacovigilance Group.
- The Investigator will attempt to establish a diagnosis of the event based on signs, symptoms, or other clinical information. Whenever possible, the diagnosis (not the individual signs/symptoms) will be documented as the AE/SAE.

Assessment of Intensity

- The intensity of AEs should be documented using NCI CTCAE version 5.0.
- For events **not listed** in the NCI CTCAE version 5.0, the intensity of AEs should be classified according to the following categories:
 - **Grade 1:** Mild; asymptomatic or mild symptoms; clinical or diagnostic observations only; intervention not indicated
 - **Grade 2:** Moderate; minimal, local, or noninvasive intervention indicated; limiting age-appropriate instrumental ADL (instrumental ADL refers to preparing meals, shopping for groceries or clothes, using the telephone, managing money, etc.)
 - **Grade 3:** Severe or medically significant but not immediately life-threatening; hospitalization or prolongation of hospitalization indicated; disabling; limiting self-care ADL (Self-care ADL refers to bathing, dressing, and undressing, feeding self, using the toilet, taking medications, and not bedridden)
 - **Grade 4:** Life-threatening consequences; urgent intervention indicated
 - **Grade 5:** Death related to AE
- An event is defined as “serious” when it meets at least one of the predefined outcomes as described in the definition of an SAE, NOT when it is rated as severe.

| Assessment of Causality |
|--|
| 
• The Investigator will assess the relationship between study intervention and the occurrence of each AE. The Investigator's assessment of the relationship of each AE to study intervention will be recorded in the source documents and the eCRF. Alternative causes, such as medical history, concomitant therapy, other risk factors, and the temporal relationship of the event to study intervention, should be considered and investigated, if appropriate. The following definitions are general guidelines to help assign grade of attribution: |
| 
– Not related: The event is clearly related to other factors, such as the participant's environment or clinical state, therapeutic interventions, or concomitant drugs administered to the participant. This is especially so when an event occurs prior to the commencement of treatment with the study intervention.– Unlikely related: The temporal association, participant history, and/or circumstances are such that study intervention is not likely to have had an association with the observed event. Other conditions, including concurrent illness, progression, or expression of the disease state, or reaction to a concomitant drug administered appear to explain the event.– Possibly related: The event follows a reasonable temporal sequence from the time of study intervention administration or follows a known response to the study intervention but could have been produced by other factors, such as the participant's clinical state, other therapeutic interventions, or concomitant drugs administered to the participant.– Probably related: The event follows a reasonable temporal sequence from the time of study intervention administration and follows a known response to the study intervention and cannot be reasonably explained by other factors, such as the participant's clinical state, other therapeutic interventions, or concomitant drugs administered to the participant.– Definitely related: The event follows a reasonable temporal sequence from the time of study intervention administration or control abates upon discontinuation or cannot be explained by known characteristics of the participant's clinical state. |

Follow-up of AEs and SAEs

- The Investigator is obligated to perform or arrange for the conduct of supplemental measurements or evaluations as medically indicated or as requested by the Sponsor to elucidate the nature or causality of the AE or SAE as fully as possible. This may include additional laboratory tests or investigations, histopathological examinations, or consultation with other health care professionals.
- If a participant dies during participation in the study or during a recognized follow-up period, the Investigator will provide BOTH EQRx International, Inc. and Parexel Pharmacovigilance Group with a copy of any postmortem findings including histopathology.
- New or updated information will be recorded in the originally completed form.
- The Investigator will submit any updated SAE data via email to BOTH [contact] and [contact] within 24 hours of receipt of the information.

10.3.4. Reporting of SAEs

Definition of a Serious Adverse Event

- An SAE is an AE occurring during any study phase (ie, baseline, treatment, washout, or follow-up) and at any dose of study intervention (active or placebo) that fulfills one or more of the following:
 - It results in death.
 - It is immediately life-threatening.
 - It requires formal inpatient hospitalization or prolongation of existing hospitalization.
 - It results in persistent or significant disability or incapacity.
 - It results in a congenital abnormality or birth defect.
 - It is an important medical event that may jeopardize the participant or may require medical intervention to prevent one of the outcomes listed above.
 - Important medical events that may not be one of the above may be considered an SAE by the Investigator when, based upon appropriate medical judgment, they are considered clinically significant and may jeopardize the participant, or may require medical or surgical intervention to prevent one of the outcomes listed above.
 - An AE is considered “life-threatening” if, in the opinion of either the Investigator or the Sponsor, its occurrence places the participant at immediate risk of death. It does not include an AE that, had it occurred in a more severe form, might have caused death.

SAE Reporting via Email

- The Investigator must report any SAEs via email to BOTH [contact] and [contact] within 24 hours of becoming aware of the event.
- The Investigator and the Sponsor (or Sponsor's designated agent) will review each SAE report, and the Sponsor/Sponsor's designated agent will evaluate the seriousness and the causal relationship of the event to study intervention. In addition, the Sponsor (or Sponsor's designated agent) will evaluate the expectedness according to the Reference Safety Information (Investigator's Brochure or Summary of Product Characteristics). Based on the Investigator and Sponsor's assessment of the event, a decision will be made concerning the need for further action.
- After the study is completed at a given site, the electronic data collection tool will be deactivated to prevent the entry of new data or changes to existing data.
- If a site receives a report of a new SAE from a study participant or receives updated data on a previously reported SAE after the electronic data capture system has been deactivated, then the site can report this information on a paper SAE Form or by telephone.
- Contacts for SAE reporting (as detailed in Section 10.3.4.1) can also be found in the Investigator site file.

SAE Reporting via SAE Form

- Email transmission of the SAE Form is the preferred method to transmit this information.
- In rare circumstances and in the absence of email equipment, notification by telephone is acceptable.
- Initial notification via telephone does not replace the need for the Investigator to complete and sign the SAE Form within the designated reporting timeframes.
- Contacts for SAE reporting (as detailed in Section 10.3.4.1) can also be found in the Investigator site file.

Serious Unexpected Serious Adverse Reactions

Any AE that is serious, associated with the use of the study intervention, unexpected, and which has a reasonable suspected causal relationship to the study intervention is considered a SUSAR and has additional reporting requirements, as described below.

- An unexpected AE is an event or reaction that is not listed in the IB or not listed at the specificity or severity that has been observed, or the nature and severity of which is not consistent with the information about the medicinal product in question as set out in the reference safety information; or, if an IB is not required or available, is not consistent with the risk information described in the General Investigational Plan or elsewhere in the relevant current Investigational New Drug Application.
- A reasonable suspected causal relationship means that there is a reasonable possibility that the study intervention caused the AE, ie, evidence to suggest a causal relationship.
- If the SUSAR is fatal or life-threatening, associated with study intervention, and unexpected, regulatory authorities and IRBs/IECs will be notified as soon as possible and in any event within 7 calendar days after the Sponsor first learns of the event or such earlier time period as required under national law.
- Additional follow-up information for fatal or life-threatening SUSARs (eg, cause of death, autopsy report, hospital report) information should be reported within an additional 8 days (15 days total).
- If the SUSAR is not fatal or life-threatening but is otherwise serious, associated with study intervention, and unexpected, regulatory authorities and IRBs/IECs will be notified as soon as possible and in any event within 15 calendar days after the Sponsor first learns of the event or such earlier time period as required under national law.
 - Additional follow-up information for non-fatal/life-threatening SUSARs (eg, hospital report) should be reported within 15 days total.
- The Sponsor will notify the Investigators in a timely fashion of relevant information about SUSARs that could adversely affect the safety of study participants. Follow-up information may be submitted if necessary.
- The Sponsor will also provide annual safety updates to the regulatory authorities and IRBs/IECs responsible for the study. These updates will include information on SUSARs and other relevant safety findings.

10.4. Appendix 4: Contraceptive and Barrier Guidance

10.4.1. Definitions

Study participants in the following categories are considered **female participants of childbearing potential (fertile/of reproductive potential)**:

1. Following menarche.
2. From the time of menarche until becoming **postmenopausal**, unless **permanently sterile** (see below).
 - A postmenopausal state is defined as no menses for 12 months without an alternative medical cause.
 - A high FSH level in the postmenopausal range may be used to confirm a postmenopausal state in female participants not using hormonal contraception or HRT. However, in the absence of 12 months of amenorrhea, confirmation with more than 1 FSH measurement is required.
 - Female participants on HRT and whose menopausal status is in doubt will be required to use one of the non-estrogen hormonal highly effective contraception methods if they wish to continue their HRT during the study. Otherwise, they must discontinue HRT to allow confirmation of postmenopausal status before study enrollment.
 - **Permanent sterilization** methods (for the purposes of this study) are defined as the following:
 - Documented hysterectomy
 - Documented bilateral salpingectomy
 - Documented bilateral oophorectomy

For individuals with permanent infertility due to an alternate medical cause other than the above, (eg, Mullerian agenesis, androgen insensitivity, gonadal dysgenesis), Investigator discretion should be applied to determining study entry.

Notes:

- Documentation can come from the site personnel's review of the participant's medical records, medical examination, or medical history interview.
- If fertility is unclear (eg, amenorrhea in adolescents or athletes) and a menstrual cycle cannot be confirmed before the first dose of study intervention, additional evaluation should be considered.

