4. STUDY DESIGN

4.1. Overall Design

This is a multicenter, single-arm, open-label study to evaluate the safety and efficacy of lerociclib administered in combination with standard endocrine therapy in female or male participants with HR+/HER2- mBC.

The study population will consist of newly diagnosed, treatment-naïve participants with HR+/HER2- mBC (collectively referred to as the first-line, or 1L, population) and participants with HR+/HER2- mBC who have already progressed on first-line endocrine therapy such as tamoxifen, anastrozole, or letrozole (collectively referred to as the second-line, or 2L, population).

Approximately 100 participants will be enrolled and dosed in the study, with approximately 50 participants enrolled and dosed for each line of therapy (1L or 2L). All premenopausal or perimenopausal female participants, and all male participants, must be receiving goserelin for at least 28 days prior to entering the study and will remain on goserelin throughout the study, in accordance with the prescribing information and according to the study site's standard practice. The schedule for administration of goserelin for each individual participant is decoupled from the rest of the study visit schedule, and will be determined by the date of the participant's most recent dose of goserelin at the time of study entry (with "goserelin C1D1" defined as the date of the participant's most recent dose + 28 days, then every 28 days subsequently).

All study participants (1L and 2L populations) will receive the Investigator's choice of AI (letrozole) or fulvestrant plus lerociclib 150 mg BID. All participants should be treated according to the best current practice guidelines and standard of care within each institution or country where the study is conducted.

The study will consist of 3 phases: a Screening Phase of up to 42 days in duration; a Treatment Phase (which includes a Safety Follow-up Visit occurring 30 days after the last dose of lerociclib); and a Post-Treatment Follow-up Phase (which includes a Survival Follow-up Phase) that will continue until death, loss of follow-up, withdrawal of consent, or the end of the study (whichever occurs first).

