5.2. Exclusion Criteria

Prospective participants are excluded from the study if **any** of the following criteria apply:

Medical Conditions

1. Has symptomatic visceral disease or any disease burden that makes the participant ineligible for endocrine therapy, per the Investigator's best judgment.
2. Has peritoneal carcinomatosis.
3. Has inflammatory breast cancer at Screening.
4. Has CNS involvement, **unless** participant is at least 4 weeks from prior therapy completion to starting study treatment, has stable CNS tumor at the time of Screening, and is not receiving steroids and/or enzyme-inducing anti-epileptic medications for brain metastases.
5. Has any clinically significant, uncontrolled heart disease and/or cardiac repolarization abnormality.
6. Has a history of prolonged QT syndrome or Torsades de Pointes.

Prior/Concomitant Therapy

7. Has received prior treatment with chemotherapy (**except** neoadjuvant/adjuvant chemotherapy), or with any CDK4/6 inhibitor.
8. Has received prior treatment with fulvestrant.
9. Use of systemic estrogens (eg, hormonal contraception, HRT).
10. Is currently receiving any of the following substances and cannot be discontinued 14 days prior to starting lerociclib:
 - Known strong or moderate CYP3A inducers or strong inhibitors of CYP3A

- Substances that have a narrow therapeutic window and are predominantly metabolized through CYP3A4/5
11. Has evidence of active bacterial infection, fungal infection, or viral infection (including SARS-CoV-2 or uncontrolled HIV, as noted below) which would preclude safe enrollment in the judgment of the Investigator.
- **Notes:**
 - The study SARS-CoV-2 requirements are determined by institutional standards (and local/country regulations, as applicable).
 - At Investigator discretion, any participant who tests positive and/or is symptomatic for SARS-CoV-2 during Screening may either be excluded from the study or delay enrollment until active infection has been excluded per institutional standards.
 - During the study, any SARS-CoV-2 testing is to be performed as clinically indicated for the individual participant. The Investigator must document the results of all tests performed. Any confirmed infection is to be recorded as an AE or, in the event that clinical manifestation warrants such, recorded and handled as an SAE as detailed in [Appendix 3](#).

Diagnostic Assessments

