10.4.2. Contraception Guidance

Note: The study exclusion criteria (Section 5.2) prohibit use of systemic estrogen, including hormonal contraception containing estrogen, in this study. Nonestrogen hormonal contraception, including progestogen-containing contraception, is permitted at Investigator discretion.

| |
|--|
| CONTRACEPTIVES^a ALLOWED DURING THE STUDY INCLUDE: |
| Highly Effective Methods^b that Have Low User Dependency Failure rate of < 1% per year when used consistently and correctly. |
| 
For female study participants of childbearing potential and male study participants' female partners who are of childbearing potential (as applicable):
 
 • Implantable progestogen-only hormone contraception associated with inhibition of ovulation^c 
 – Intrauterine device – intrauterine hormone-releasing system^c – Bilateral tubal occlusion |
| Highly Effective Methods^b that are User-Dependent Failure rate of < 1% per year when used consistently and correctly. |
| 
For female study participants of childbearing potential and male study participants' female partners who are of childbearing potential (as applicable):
 
 • Non-estrogen hormonal contraception (progestogen-containing contraception is permitted at Investigator discretion) associated with inhibition of ovulation^c 
 – oral – intravaginal – transdermal – injectable |
| 
 • Progestogen-only hormone contraception associated with inhibition of ovulation^c 
 – oral – injectable |
| 
For female study participants of childbearing potential:
 
 • Sexual abstinence 
Sexual abstinence is considered a highly effective method only if defined as refraining from heterosexual intercourse during the entire period of risk associated with the study intervention.
 
The reliability of sexual abstinence needs to be evaluated in relation to the duration of the study and the preferred and usual lifestyle of the participant.
 |

| |
|---|

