| 
Effective Methods^d that are Not Considered Highly Effective Failure rate of $\geq 1\%$ per year when used consistently and correctly.
 
For female study participants of childbearing potential and male study participants' female partners who are of childbearing potential (as applicable):
 
 • Progestogen-only oral hormonal contraception, where inhibition of ovulation is not the primary mode of action • Male or female condom with or without spermicide • A combination of male condom with either cervical cap, diaphragm, or sponge with spermicide (double-barrier methods)^c 
 – Note: Male participants with female partners who are of childbearing potential are to use a male condom throughout their study treatment and for at least 365 days (1 year) after the last dose of any study intervention, even if azoospermic (whether vasectomized or due to a medical cause). • Cervical cap, diaphragm, or sponge with spermicide |
| 
Additional Contraception Guidance During and for at Least 1 Year after Treatment with Fulvestrant
 
For male study participants:
 
 • Highly effective contraception is to be used during treatment with fulvestrant and for at least 365 days (1 year) after the last dose of fulvestrant, as recommended in the FDA-approved prescribing information (FASLODEX[®] (fulvestrant), rev. 05/2019). 
For female study participants of childbearing potential:
 
 • Highly effective contraception is to be used during treatment with fulvestrant and for at least 365 days (1 year) after the last dose of fulvestrant, as recommended in the FDA-approved prescribing information (FASLODEX[®] (fulvestrant), rev. 05/2019). |
| 
Additional Contraception Guidance During and for 12 Weeks after Treatment with Goserelin
 
For female study participants of childbearing potential:
 
 • Highly effective nonhormonal contraception is to be used during treatment with goserelin and for 12 weeks after the last dose of goserelin, as recommended in the FDA-approved prescribing information (ZOLADEX[®] [goserelin], rev. 02/2015). |

^a. Contraceptive use by female and male study participants should be consistent with local regulations regarding the use of contraceptive methods for those participating in clinical studies.

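### Appendix 4 lets some women continue HRT that Exclusion Criterion 9 bars, and lists hormonal contraception for women whose mandatory goserelin calls for nonhormonal methods

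*Protocol*

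**What the plan says.** **HRT**

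- Protocol section 5.2, Exclusion Criterion 9, excludes: "Use of systemic estrogens (eg, hormonal contraception, HRT".
- The note that opens section 10.4.2 repeats the ban: "The study exclusion criteria (Section 5.2) prohibit use of systemic estrogen, including hormonal contraception containing estrogen, in this study".
- Section 10.4.1 says of HRT users with uncertain menopausal status that they "will be required to use one of the non-estrogen hormonal highly effective contraception methods if they wish to continue their HRT during the study". The next sentence gives the alternative: "Otherwise, they must discontinue HRT to allow confirmation of postmenopausal status before study enrollment".

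**Contraception**

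- Section 10.4.1 defines childbearing potential as running "From the time of menarche until becoming" postmenopausal, unless the woman is permanently sterile.
- Section 4.1, repeated in section 6.1, states: "All premenopausal or perimenopausal female participants, and all male participants, must be receiving goserelin for at least 28 days" before entry, and they stay on it throughout the study.
- The section 10.4.2 note says: "Nonestrogen hormonal contraception, including progestogen-containing contraception, is permitted at Investigator discretion". The table below it lists progestogen implants, a hormone-releasing intrauterine system, and oral, vaginal, transdermal and injectable hormonal methods. It lists them for female participants of childbearing potential and for male participants' female partners alike.
- The goserelin row of the same table, addressed to female participants of childbearing potential, says: "Highly effective nonhormonal contraception is to be used during treatment with goserelin and for 12 weeks after the last dose of goserelin".
- Inclusion Criterion 9 (section 5.1) asks these women to use contraception in line with the prescribing information for fulvestrant or goserelin, where applicable. It sends the reader to Appendix 4 for the definitions and methods.

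**The concern.** Sites are sent to Appendix 4 to decide who is of childbearing potential and which methods are acceptable, so its text will be used. On HRT, it offers a route to staying on a treatment that the exclusion criteria name as barred. A site that relied on it could produce an eligibility deviation. A site that relied on section 5.2 would turn the same woman away or ask her to stop HRT. On contraception, two rows of one table give the same woman different instructions.

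At stake is whether sites admit the same participants and accept the same hormonal exposures. Section 2.2 describes estrogen deprivation as the centerpiece of therapy in this disease, and section 6.3 confirms that there is no comparator, so the hormonal background should be defined once. Contraception was also the main reason for Amendment 3, so this is guidance that sites can expect to be unambiguous.

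**Working it through.** The plan gives no figure on this point, so the check is a comparison of texts.

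**Step 1. HRT, by type of user**

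| Participant | Section 5.2 | Section 10.4.1 | Result |
|---|---|---|---|
| Systemic estrogen HRT, menopausal status in doubt | Excluded | May continue with a non-estrogen hormonal contraceptive | Contradiction |
| Non-estrogen or non-systemic HRT, status in doubt | Arguably not reached, since HRT is named as an example of systemic estrogen | May continue on the same condition | Can be reconciled |
| HRT user, status not in doubt | Excluded if systemic estrogen | Sentence does not apply | No contradiction |

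The first row is the problem. Section 10.4.1 refers to HRT without qualification, so nothing in it confines the permission to the second row. Stopping HRT appears only as the alternative, so continuing is a real option in the text.

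**Step 2. Contraception, by inference from definitions**

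1. A woman of childbearing potential is not yet postmenopausal (10.4.1).
2. She is therefore pre- or perimenopausal. The protocol does not define perimenopausal, so this is an inference.
3. All pre- or perimenopausal women must take goserelin before entry and throughout (4.1, 6.1).
4. The goserelin row therefore applies to her and calls for a highly effective nonhormonal method.
5. The rows above it list hormonal methods as allowed for her.

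**Step 3. When the two contraception rules conflict**

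- During goserelin and for 12 weeks after: 12 × 7 = 84 days. A hormonal method alone meets the general rows but not the goserelin row.
- If all study treatment ends together, from day 85 to day 365 of the one-year post-treatment period (365 − 84 = 281 days) only the general rows apply, and there is no conflict.
- A woman using a listed nonhormonal method (a nonhormonal intrauterine device, bilateral tubal occlusion or abstinence) meets both rules throughout.
- Male participants' female partners are outside the goserelin row, so there is no conflict for them.

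**Step 4. Where the two conflicts meet**

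For a woman who continues HRT, section 10.4.1 goes beyond allowing a hormonal method: it requires one. If her doubtful status means that she is managed as of childbearing potential, she must take goserelin, and the goserelin row requires a nonhormonal method. No single method satisfies both. Using one of each would meet both sentences literally, but nothing says that this is intended.

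**Step 5. Does another section settle it?**

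Section 6.9, on concomitant therapy, does not mention systemic estrogens or progestogens. No section states an order of precedence between Appendix 4 and section 5, or between rows of the contraception table.

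**The case against.** **On HRT.** Appendix 4 classifies childbearing potential; it does not admit anyone. Participants must meet no exclusion criterion, waivers are forbidden (sections 5 and 8), and eligibility is checked at Screening and again at Cycle 1 Day 1. Section 10.4.2 restates the systemic-estrogen ban soon after the HRT sentence. All of this stands. It makes it unlikely that many women on systemic estrogen would be enrolled, and the documents do not support saying that sites would enrol them. It does not remove the sentence, which still sets terms for continuing HRT during the study.

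**On contraception.** A general list can be narrowed by a specific rule. The goserelin row is headed as additional guidance, and Inclusion Criterion 9 points to the goserelin prescribing information, so a careful site would probably let that row prevail. The hormonal rows would keep a use for male participants' partners and after the 12-week period. This is a fair reading and the reason that this half is the lesser point. But the protocol does not state it, and the table still names female participants under the hormonal methods without a cross-reference.

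**On consequences.** The primary endpoint is the incidence of adverse events, and no hypothesis is tested. The listed hormonal methods are classed as highly effective, condoms must be added to them, and pregnancy is tested on Day 1 of every cycle. This stands, and it limits what can be claimed.

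**Conclusion.** Both contradictions are in the current protocol text. The HRT sentence is the more serious, because it sets terms for something that an exclusion criterion names as barred. The contraception conflict is real as worded, but Inclusion Criterion 9 suggests how to resolve it.

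Those affected are women who would use HRT with doubtful menopausal status, probably few, and women of childbearing potential who would choose a hormonal method. The documents give neither number. The contraception half rests on the inference that childbearing potential implies pre- or perimenopausal status.

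Three stronger readings are tempting and are not supported:

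- *Every woman of childbearing potential is affected.* The wording reaches essentially all of them, but only those who would use a hormonal method face a conflict.
- *Response or progression-free survival would be distorted.* With about 40 evaluable participants per line, one participant weighs 1/40 = 2.5 percentage points of ORR. That is the weight of any participant and not an estimated effect. The documents contain no data on what HRT or progestogen use would do to either endpoint in this trial.
- *Contraceptive protection is weakened.* Both kinds of method are listed as highly effective, and nothing shows a loss of protection.

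Sample size and analysis methods are unaffected. The correction is worth making because it settles which participants and exposures sites accept.

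**What to change.** 1. Reconcile the HRT sentences in section 10.4.1 with Exclusion Criterion 9 so that HRT has one status. If the sponsor intends to distinguish types of HRT, both places should say so.
2. Reconcile the hormonal-method rows and the opening note of section 10.4.2 with the goserelin row. State which governs during goserelin and in the 12 weeks after it, and align the hormonal-method requirement for women on HRT in section 10.4.1.
3. List separately the methods that apply only to male participants' female partners.
4. Carry the resulting status of systemic estrogens and progestogens into section 6.9.
5. Flag any on-study HRT or hormonal contraceptive use from the concomitant-medication data already collected, and review it with the protocol deviations under SAP section 4.4.2 where it breaks the reconciled rule.

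The sponsor decides the clinical rule; the request is only that the passages agree. The cost is wording in Appendix 4, section 6.9 and, if needed, section 5.2, plus a flag on existing data. No visits or tests are added.
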